6.1. SUMMARY STATISTICS

For qualitative variables, the population size (N for sample size and n for available data) and the percentage (of available data) for each class of the variable will be presented. Quantitative variables will be summarized using descriptive statistics, including N (with data available), mean, standard deviation (SD), median, Q1, Q3, minimum, and/or maximum values. Geometric mean will be included for immunogenicity parameters together with 95% confidence interval (CI), where applicable.

The exact two-sided 95% CIs for a proportion within a group will be calculated using the Clopper-Pearson exact method. The geometric mean antibody concentrations (GMCs) and titers (GMTs) calculations will be performed by taking the anti-log of the mean of the log10 titer transformations. Confidence interval for geometric means will be derived by raising 10 to the confidence interval associated with mean of log10 values i.e., CI of geometric mean = $10^{(CI \text{ for the mean of log10 values})}$. All participants with valid data will be considered. Participants whose antibody titers are below the cut-off of the assay will be given an arbitrary value of half the cut-off for the purpose of GMC/GMT calculation.

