15. IMMUNOGENICITY ANALYSIS

The immunogenicity analysis will be based on the Per-protocol Set for analysis of immunogenicity. If, in any study group at any time point, the percentage of vaccinated participants with serological results excluded from the Per-protocol Set for analysis of immunogenicity is 10% or more, a second-line analysis based on the Full Analysis Set will be performed.

Numerical serology results will be derived from the content of IS.ISORRES in the SDTM dataset. For assays with a specific cut-off, the following derivation rules apply:

IS.ISORRES	Derived value
“NEG”, “-”, or “(−)”	cut-off/2
“POS”, “+”, or “(+)”	cut-off
“< value” and value is <= assay cut-off	cut-off/2
“< value” and value is > assay cut-off	value
“> value” and value is < assay cut-off	cut-off/2
“> value” and value is >= assay cut-off	value
“value” and value is < cut-off	cut-off/2
“value” and value is >= cut-off	value
All other cases	missing

Document: \\dccar2dnetvnasc01p-lan1.quintiles.net\cp_ops\PROJECTS\Glaxo SmithKline\GSK216152_WZA10802\SAP
Author: PPD Version Number: 2.0
Version Date: 07DEC2023

Template No: CS_TP_BS016 – Revision 7
Effective Date: 01Nov2021

Reference: CS_WI_BS005

The following derivation rules will apply in the context of LLOQ values:

- If baseline value is below LLOQ
 - 4-fold is defined as 4 times the LLOQ cut-off value
 - GMR is defined as within-participant GMR against LLOQ/2
- If baseline value is above or equal to LLOQ
 - 4-fold is defined as 4 times the baseline value
 - within-participant GMR is defined as within-participant GMR against the baseline value.

The following immunogenicity variables will be assessed:

Assay Type	Sampling Time Points	Component	Method	Unit of Measure	Number of Participants
Humoral Immunity (Antibody determination)	Stage 1: Days 1, 29, 57, 85, 169 and 197	Anti-S. Typhi Vi Ag total IgG	ELISA	EU/mL [#]	50 (Stage 1) 105 (Stage 2)
		Anti-S. Typhimurium O Ag total IgG		EU/mL	
		Anti-S. Enteritidis O Ag total IgG		EU/mL	

[figure not shown]
CCI

Document: \\dccar2dnetvnasc01p-lan1.quintiles.net\cp_ops\PROJECTS\Glaxo SmithKline\GSK216152_WZA10802\SAP
 Author: PPD Version Number: 2.0
 Version Date: 07DEC2023

Template No: CS_TP_BS016 – Revision 7
 Effective Date: 01Nov2021

Reference: CS_WI_BS005

CCI

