The IgG against Vi antigen will be determined using GVGH ELISA and the results will be presented in EU/mL unit, which may be further converted to µg/mL, based on correlation with concentration of the standard calibrated against the international standard/another standard already calibrated.

A listing of collection dates and times for the immunogenicity variables will be presented for participants within each treatment group. For each component, the concentration/titer will be listed and summarized by treatment groups across all scheduled timepoints during entire study for each stage. Antibody concentrations/titers for all components will be investigated using Reverse Cumulative Distribution Curves based on the Per-protocol analysis set.

For each study group, each stage, at each timepoint that blood samples are collected for humoral immune response and for each component as measure by ELISA and CCI

- Geometric mean concentrations/titers and their 95% CI will be calculated.
- Within-participant geometric mean ratio (geometric mean at 28 days after each study intervention to each study intervention administration baseline, ie, Day 29 versus Day 1, Day 85 versus Day 57 and Day 197 versus Day 169 and to Day 1 baseline) with their 95% CI will be tabulated.
- Percentage of participants with ≥ 4 fold-increase from Day 1 baseline with their exact 95% CI will be calculated.
- Unadjusted between-group ratio of GMC with 95% CI between iNTS-TCV groups and iNTS-GMMA and TCV groups will be computed for each anti-serotype specific IgG^{1*}, visit, and administration. The unadjusted ratios for each visit will be calculated using results from the corresponding visit as the dependent variable and the treatment group as independent variable. No other covariates will be included in the model.

For each study group, each stage, at each timepoint for S. Typhi Vi component as measured by ELISA:

- The number and percentage of participants with Anti-S. Typhi Vi Ag IgG antibody concentrations \geq CCI and their 95% exact CI will be calculated.
- The number and percentage of participants with Anti-S. Typhi Vi Ag IgG antibody

¹ * Anti- Salmonella Typhi (S. Typhi) Vi antigen (Ag) total IgG, Anti Salmonella Typhimurium (S. Typhimurium) O Ag total IgG, Anti Salmonella Enteritidis (S. Enteritidis) O Ag total IgG will be tested.

concentrations \geq [CC1] and their 95% exact CI will be calculated.

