The above tabulations may be performed by LLOQ status at baseline (above or equal to cut-off versus below the cut-off) for all 3 components, data permitting.

Only for S. Typhi Vi component the above tabulations may be performed by Anti-S. Typhi Vi Ag IgG antibody concentrations status at baseline as measured by ELISA ($>=$ [CC1] and $<=$ [CC1], $>=$ [CC1] and $<=$ [CC1]), data permitting.

Linear mixed model with repeated measures (MMRM) will be used to perform pairwise comparison between full doses of iNTS-TCV and iNTS-GMMA + TCV at Day 29, Day 57, Day 85, Day 169 and Day 197. The model will use fixed effects for center, treatment, time point, treatment*time point, center*treatment, baseline immunogenicity value as covariate, and a repeated time point effect within a participant under an unstructured covariance matrix. Variance between the groups will not be considered equal unless the assumption leads to convergence issues. Additional covariance structures and suitable transformation (e.g., log) may be explored to attain convergence and meet model assumptions, respectively. This analysis will be performed for full doses of iNTS-TCV and iNTS-GMMA + TCV from both the stages.

```
proc mixed data=indsn;  by parameter;  
  class subjid center trta avisit;  
  model aval=center trta avisit trta*avisit center*trta baseline/ddfm=satterth;  
  repeated avisit/subject=subjid type=un group=trta;  
  lsmeans trta*avisitn/pdiff cl alpha=0.05;  
  run;
```

In this analysis, immunogenicity data from full dose group in Europe will be pooled with those from full dose group in Africa if p-value associated to parameter for center*treatment interaction from MMRM model ≥ 0.10 (i.e., suggesting that impact of treatment on immunogenicity endpoint does not depend on center). In that case, GMC, GMRs, and ratio of GMC will be calculated for entire full dose group (i.e., Europe + Africa) adjusted by center from the above MMRM model without the center*treatment interaction term.

In case center*treatment interaction term is significant (i.e., p-value <0.1) the following analyses will be performed: 1) main analysis including center*treatment interaction term and GMC ratio separately for Europe and Africa will be produced from model with center*treatment interaction term, 2) sensitivity analysis excluding center*treatment interaction and GMC ratio for pooled Europe and Africa will be produced from model without center*treatment interaction term.

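### SAP Section 15 analyses a '< value' result above the cut-off as the bound itself, so left-censored samples can be scored as responders and left-censored baselines can hide a response

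*SAP*

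**What the plan says.** SAP Section 15 has a table that turns the reported serology result into a number, for assays with a specific cut-off. Four of its rows matter here:

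- "< value” and value is <= assay cut-off": derived as half the cut-off.
- "< value” and value is > assay cut-off": derived as the value.
- "> value” and value is >= assay cut-off": derived as the value.
- The mirror row, a `>` result whose value is below the cut-off: derived as half the cut-off.

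The same section then sets the 4-fold rule. If baseline is below LLOQ, "4-fold is defined as 4 times the LLOQ cut-off value"; otherwise "4-fold is defined as 4 times the baseline value". The reported percentage counts participants at or above a 4-fold rise: "fold-increase from Day 1 baseline with their exact 95% CI will be calculated". The SAP treats LLOQ and cut-off as one quantity, as in the optional tabulations by "LLOQ status at baseline (above or equal to cut-off versus below the cut-off".

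SAP Section 6.1 adds that "Participants whose antibody titers are below the cut-off of the assay will be given an arbitrary value of half the cut-off", and Section 7.2.7 repeats this. Section 7.2.7 also leaves the numerical cut-off to the laboratory, to be set before the analysis. Neither document flags, queries or excludes a `<` result with a bound above the cut-off.

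**The concern.** A `<` result means that the concentration is below the stated bound. Assigning the bound gives the sample the one number at the edge of its range that it cannot have. A `>` result with the same bound gets the same number, so opposite information becomes identical data. A `<` result at or below the cut-off is halved, and the SAP gives no reason for treating the two sides of the cut-off differently.

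The derived numbers feed the secondary immunogenicity endpoints in Protocol Section 3: GMCs, within-participant GMRs, the 4-fold seroresponse and the Vi threshold percentages. They also enter the between-group ratios, the reverse cumulative curves and the baseline covariate of the repeated-measures model. The responder endpoints are defined by 'at or above', so substituting the bound pushes results toward the responder side after vaccination and raises the bar when it happens at baseline. A `<` baseline above the cut-off would also be placed in the stratum at or above LLOQ, although it may belong below it.

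**Working it through.** The plan gives no figure to reproduce. The check applies the written rules to example results.

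**Inputs.** The derivation rows, the 4-fold rules and the at-or-above count come from SAP Section 15. Group sizes (45 in each Stage 2 vaccine group, 16 in each Stage 1 full-dose group) come from Protocol Table 4, and the 12% dropout from Protocol Section 9.2. The cut-off is not given; cut-off = LLOQ = 50 EU/mL is assumed for illustration.

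**Post-dose result censored.** With baseline below LLOQ, the target is 4 × 50 = 200.

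| Post-dose result | Derived | Scored | What is known |
|---|---|---|---|
| `199` | 199 | non-responder | non-responder |
| `<199` | 199 | non-responder | non-responder |
| `<200` | 200 | responder | non-responder |
| `>200` | 200 | responder | responder |
| `<400` | 400 | responder | undetermined |

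The within-participant ratio for both `<200` and `>200` is 200/25 = 8. The same happens above LLOQ: baseline 60 with post-dose `<240` is derived as 240 = 4 × 60 and scored as a responder, although the sample is known to be below 240.

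The Vi threshold works the same way. A `<` result with a bound at or above the threshold counts as reaching it.

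**Baseline censored.** Baseline `<150` is derived as 150, so the target becomes 4 × 150 = 600. A post-dose 300 is then a non-responder (300/150 = 2). If the true baseline is below 50, the target is 200 and 300 is a response. For true baselines from 50 to 75 it is still a response, because 4 × 75 = 300. Above 75 it is not. The status is undetermined but scored negative.

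**Mirror row.** With cut-off 50, `>40` becomes 50/2 = 25, although the sample is known to exceed 40.

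**Size per result.** Replacing v by v/2 for one participant in a group of n changes the GMC by the factor 2^(1/n), whatever v or the cut-off.

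- Stage 2 vaccine group: 45 × 0.88 = 39.6, about 40. GMC inflation 2^(1/40) − 1 = 1.7%. Seroresponse shift 1/40 = 2.5 points.
- Stage 1 full-dose group: 16 × 0.88 = 14.1, about 14. GMC inflation 2^(1/14) − 1 = 5.1%. Seroresponse shift 1/14 = 7 points.

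A censored baseline moves the GMR the other way by the same factor.

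**The case against.** The strongest objection is that the case may never arise. Protocol Section 8.1.2 calls for qualified assays at the GVGH laboratory or one it designates, and the laboratory fixes the cut-off beforehand. A sample below a single cut-off would be reported as `< cut-off`, which the table halves. Neither document mentions starting dilutions or sample-specific limits, and the mirror row needs a `>` bound below the lower cut-off. This stands as a limit on importance, not on correctness: the SAP wrote rows for these cases, so the rows should give a defensible value.

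Three stronger readings are tempting, and the documents do not support them.

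- A reader might infer that the rule generally counts proven non-responders as responders. That needs the bound to equal the target exactly. With a larger bound the true status is unknown; with a smaller one the sample is not counted. For Vi, the Protocol's 4.3 µg/mL threshold applies after conversion from EU/mL, so nothing in the documents suggests an exact tie.
- A reader might measure the GMC shift against half the cut-off. For a bound of four times the cut-off that is an 8-fold difference, giving 8^(1/40) − 1 = 5% and 8^(1/14) − 1 = 16%. But `<200` with cut-off 50 is not known to be below 50, so half the cut-off is the wrong comparator. Half the bound gives 1.7% and 5.1%.
- A reader might see a contradiction with SAP Sections 6.1 and 7.2.7. Those cover results below the cut-off, which a `<200` result has not been shown to be. The treatment is uneven, not contradictory.

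Using the bound for a `>` result at or above the cut-off is a common convention and is not at issue. The stakes are also limited: Protocol Section 9.1 tests no formal hypotheses, Section 9.6.2 calls the comparisons exploratory, and the concentrations are listed by participant.

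**Conclusion.** The concern holds in a limited form. As written, SAP Section 15 gives left-censored results above the cut-off a number they are known not to reach, and it can give the mirror case a number below what the sample is known to exceed. After vaccination this can score a participant of unknown status as a responder or, at an exact tie, a certain non-responder. At baseline it overstates the starting level and can hide a response. The bias therefore does not run in one direction.

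The sizes above are per result and take half the bound as the alternative. They rest on 12% dropout. The 50 EU/mL cut-off only illustrates the rules, and the GMC figures do not depend on it. The total effect cannot be stated, because the documents do not say how often such results will be reported. It may be rarely or never.

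**What to change.** Amend SAP Section 15 as follows.

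1. Derive a `<` result with a bound above the cut-off as half the bound for GMC and GMR, in line with the existing half-cut-off rule.
2. Classify responders from the bounds, not from the substituted number.
   - Post-dose `<` result: non-responder if the bound is at or below the target; missing if the bound is above it.
   - Baseline `<` result: consider every possible baseline from below LLOQ up to the bound, and assign a status whenever all give the same answer. With baseline `<150` and cut-off 50, a post-dose value of at least 600 is a responder, one below 200 is a non-responder, and only values between are missing. Setting every such participant to missing would discard outcomes that are known.
   - Apply the same bound logic to the Vi thresholds.
3. Set a `>` result with a bound below the cut-off to missing.
4. List every result handled by these rows.

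The cost is a few lines of SAP text and programming, with no new data collection. The downside is that a few responder statuses may become missing. If no such results occur, nothing changes.

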	
 The number and percentage of participants with at least a 4-fold increase in Anti-serotype specific IgG* antibody concentration 28 days after each study intervention administration compared to first study intervention administration baseline, with exact 95% CI as measured by in-house ELISA. The number and percentage of participants with Anti-S. Typhi Vi Ag IgG antibody concentrations equivalent to $\geq 4.3 \mu\text{g/mL}$, before and 28 days after each study intervention administration, with 95% CI as measured by in-house ELISA. Unadjusted between-group ratio of GMC with 95% CI between iNTS-TCV groups and iNTS-GMMA and TCV groups will be computed for each anti-serotype specific IgG*, visit, and administration. 
* Anti-S. Typhi Vi Ag total IgG, Anti-S. Typhimurium O Ag total IgG, Anti-S. Enteritidis O Ag total will be tested.
 
The GMCs, GMRs, and ratio of GMC along with 95% CIs will be obtained by exponentiating (base 10) the means and the lower and upper limits of the 95% CIs of the log-transformed values (base 10).
 
For the between-group assessments, the ANOVA model will be fitted based on the participants having a result at both the baseline and the considered time point. Immunogenicity data from full dose group in Europe will be pooled with those from full dose group in Africa if p-value associated to parameter for Center*Treatment interaction from ANOVA model ≥ 0.10 (ie, suggesting that impact of treatment on immunogenicity endpoint does not depend on center).
 
In that case, GMC, GMRs, and ratio of GMC will be calculated for entire full dose group (ie, Europe + Africa) adjusted by center. ANOVA model will include both vaccine group and center group as fixed effects, and adjusted GMC, GMRs, and ratio of GMC will be derived by exponential transformation of the corresponding group contrast in the model.
 
A sensitivity analysis will be performed pooling Europe and Africa data and adjusting treatment effect for center variable, regardless of the center*treatment associated p-value.
 
A second sensitivity analysis will be performed pooling Europe and Africa and adjusting treatment effect for race variable.
 
Finally, subgroup analysis will be performed by race.

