The following Table summarizes the statistical analyses:

Document: \\dccar2dnetvnasc01p-lan1.quintiles.net\cp_ops\PROJECTS\Glaxo SmithKline\GSK216152_WZA10802\SAP
Author: PPD Version Number: 2.0
Version Date: 07DEC2023

Template No: CS_TP_BS016 – Revision 7
Effective Date: 01Nov2021

Reference: CS_WI_BS005

Starting Model	P-value for Center*Treatment Interaction	Main Analysis Model	Sensitivity Analysis
center, treatment, center*treatment	≥0.1 drop center*treatment from the model	Starting model without center*treatment term	No sensitivity analysis
time point, treatment*time point, baseline immunogenicity value as covariate	<0.1	Same as the starting model. Output GMC ratio from model with interaction, separately from Europe and Africa	Starting model without center*treatment term

In other words, analysis pooling Europe and Africa data adjusting treatment effect for center variable will be performed in all cases, however in case center*treatment interaction parameter is statistically significant at 0.1 level, it will be considered as sensitivity analysis.

A sensitivity analysis may also be performed pooling Europe and Africa and adjusting treatment effect for race variable if there is evidence of different races at the two centers.

CCI

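### The MMRM behind the separate Europe and Africa GMC ratios has no center*treatment*visit term, so the two ratios can differ only by one factor common to all visits, and the printed code cannot output them

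*SAP*

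**What the plan says.** SAP section 15 compares the full-dose combined vaccine with the separately given vaccines at Days 29, 57, 85, 169 and 197, using both stages. The mean model is: "The model will use fixed effects for center, treatment, time point, treatment*time point, center*treatment, baseline immunogenicity value as covariate". The MODEL statement has the same terms. Neither has center*visit or center*treatment*visit.

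If the center*treatment p-value is below 0.10, the SAP's first output is: "main analysis including center*treatment interaction term and GMC ratio separately for Europe and Africa will be produced from model with center*treatment interaction term". The summary table in the same section keeps the starting model unchanged and says: "Output GMC ratio from model with interaction, separately from Europe and Africa".

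The code declares "class subjid center trta avisit" and requests "lsmeans trta*avisitn/pdiff cl alpha=0.05". It has no other output statement.

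On scale, the paragraph says: "Additional covariance structures and suitable transformation (e.g., log) may be explored to attain convergence and meet model assumptions, respectively". On covariance: "Variance between the groups will not be considered equal unless the assumption leads to convergence issues".

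Protocol 9.4.2 planned something else: "the ANOVA model will be fitted based on the participants having a result at both the baseline and the considered time point". SAP 3.3, which lists changes from the protocol, mentions only the Entered Set.

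**The concern.** The SAP splits the result by region when the treatment ratio appears to depend on center. The model it then uses allows that dependence in one form only: the same multiplicative gap at every visit. Regional estimates at a given visit therefore borrow the gap from the other visits.

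Protocol 4.2 gives the effect of environmental exposure on the immune response as a reason for using two settings. A gap that changes over three doses is therefore possible. If it does change, the model spreads an early gap into Day 197, or dilutes a late one. Stage 2 Day 197 is the comparison for which Protocol 9.2 chose the sample size, and the reader would then hold an adjusted Stage 2 ratio that disagrees with the unadjusted one.

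**Working it through.** **1. Group sizes.** Protocol 9.2 states 133 evaluable out of 155, with 12% dropout in each group. Taking 88% of each of the nine groups in Table 4 and rounding down gives 3+3+1+14+14+7+39+39+13 = 133, which reproduces the figure. (Without rounding by group, 155 × 0.88 = 136.4.) The full-dose groups are then 14 per arm in Europe and 39 per arm in Africa, 53 per arm in all.

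**2. Algebra.** On the log scale, the treatment contrast in center c at visit t is

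(treatment) + (treatment*visit at t) + (center*treatment for c).

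Subtracting Europe from Africa cancels the first two parts, and what remains contains no t. The five visit-specific Africa-minus-Europe contrasts have rank 1 in the SAP model, rank 1 if only center*visit is added, and rank 5 once center*treatment*visit is added. In one simulated dataset, the fitted Africa/Europe ratio of ratios was 1.904 at all five visits. With both terms added it was 2.00, 3.62, 1.99, 1.75 and 1.27.

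**3. Size of the bias.** The documents give no SD or correlation, so these are assumptions: log10 residual SD 0.5 after baseline, complete data, the same covariance in both arms, and correlation either exchangeable (0.4–0.8) or AR(1) (0.6–0.8). Let e and a be the true log10 treatment ratios in Europe and Africa. With exchangeable correlation the expected estimates are

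- m(t) = [14 e(t) + 39 a(t)] / 53
- D = mean over the five visits of a(t) − e(t)
- Africa at t: m(t) + (14/53) D
- Europe at t: m(t) − (39/53) D

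Example: Europe 0.5 at Days 29–169 and 1.0 at Day 197, Africa 1.0 throughout. Then m(197) = 0 and D = (4/5) × 0.301 = 0.2408. Africa is 10^(0.2642 × 0.2408) = 1.16. Europe is 10^(−0.7358 × 0.2408) = 0.66. Both should be 1.0. The last two columns give the range over all the correlations assumed.

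| True Europe ratio (Africa 1.0 throughout) | True Day 197, Europe / Africa | Model Day 197, Europe | Model Day 197, Africa |
|---|---|---|---|
| 0.5 at Days 29–169, then 1.0 | 1.0 / 1.0 | 0.66–0.73 | 1.12–1.16 |
| 0.8 at Days 29–169, then 1.0 | 1.0 / 1.0 | 0.88–0.90 | 1.04–1.05 |
| Even log-scale rise from 0.5 to 1.0 | 1.0 / 1.0 | 0.78 | 1.10 |
| 0.5 at every visit | 0.5 / 1.0 | 0.50 | 1.00 |

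These are averages over all trials, not only those with p<0.10.

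**4. Code.** The LSMEANS line uses avisitn, which is in neither CLASS nor MODEL, so it matches no effect in the model. Read as avisit, the treatment-by-visit means average over the two centers and give one ratio per visit. No statement asks for a treatment difference within a center. ESTIMATE statements could supply one, but under this model the result would still carry the constant factor.

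**5. Cost of the extra terms.** With both terms, the Day 197 standard error in Africa is 0.5 × √(2/39) = 0.113 log10, against 0.105–0.111 in the SAP model: 2–7% larger. In Europe it is 0.5 × √(2/14) = 0.189, against 0.150–0.178: about 6.5–26% larger.

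**The case against.** **Consequence.** The trial tests no hypotheses, and both documents call the comparisons exploratory and unpowered. The unadjusted ratios by stage and visit in SAP section 15 come from a separate model for each visit and do not carry this constraint. Both points stand and they limit the priority. They do not make the restricted estimate sound where the SAP calls it the main analysis.

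**The pattern is assumed.** Nothing in the documents points to a 2-fold Europe deficit that vanishes at Day 197. With 0.8 in place of 0.5 the Africa error is 4–5%, and only 12–14% of trials would reach p<0.10, against 10% with no center difference. This stands: the constraint is certain, but its size is not known.

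**Parsimony.** If the center difference is constant, the SAP model is unbiased and its single test is the stronger one: for a constant 0.5 it gives p<0.10 in 44–61% of trials, against 39% for a test at Day 197 alone. A reader might infer that pooling should be decided visit by visit. These figures do not support that.

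**Figures among split trials.** A reader might also cite results only from trials with p<0.10. In the first pattern these average about 0.46–0.54 (Europe) and 1.25–1.32 (Africa). In the same trials the fuller model also misses 1.0, giving 0.69–0.79 and 1.09–1.14. Part of that error is therefore selection on the p-value and must not be charged to the missing term.

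**Scale and output.** It would go too far to say that the SAP abandons the log scale. Protocol 9.4.2 and SAP 6.1 and 7.2.7 define GMCs through log10, so the loose sentence in section 15 needs only tightening. Nor does the SAP say outright that the regional ratios are given by visit; that is inferred from the five visits named in the same analysis. The table shells, which might settle it, are not in the documents reviewed.

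**Conclusion.** The point holds as a limitation of the model and a fault in the code. The constant factor follows from the listed fixed effects and the log scale that a GMC ratio requires; it needs no assumption about SD or correlation. The printed code does not deliver the regional ratios that the text promises.

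Bias arises only if the center difference in the treatment ratio changes over visits. Under the stated assumptions, the average error in the Stage 2 Day 197 ratio is 4–5% to 12–16% for the two patterns that end abruptly, and zero for a constant difference. A reader might infer that the Stage 2 Day 197 comparison is lost. It is not: the unadjusted estimate remains, and no formal conclusion depends on the MMRM. Priority is low to moderate. The change is a cheap improvement.

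**What to change.** - **Pooling test:** keep it as the single center*treatment test from the SAP's existing starting model.
- **Center-specific ratios:** fit a second model with log10 response and log10 baseline, adding center*avisit and center*trta*avisit. Adding center*avisit alone would not lift the constraint.
- **Code:** replace avisitn with avisit, and output treatment differences within each center and visit, by LSMEANS on center*trta*avisit or by ESTIMATE statements.
- **Reporting:** give the Stage 2 Day 197 ratio from this second model whatever the pooling p-value, beside the pooled ratio. State whether regional ratios are reported at every visit.
- **Housekeeping:** list the move from ANOVA by time point to MMRM in SAP 3.3.

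The cost is SAP wording and code, with eight more mean parameters (four for each added term). Under the assumptions above, the Stage 2 Day 197 standard error rises by 2–7%. The Europe one rises by about 6.5–26%, which leaves a Europe 95% interval of roughly the estimate multiplied or divided by 10^(1.96 × 0.189) = 2.35. These costs treat the covariance as known; the SAP estimates an unstructured matrix in each arm, so the actual figures may differ somewhat.

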9.2 Sample Size Determination

A total of 155 participants are planned to be randomized to achieve at least 133 evaluable participants in the Per Protocol analysis set for immunogenicity, assuming a 12% dropout rate for each group. Participants who withdraw from the study will not be replaced.

No confirmatory objectives are planned in this trial; however, the sample size was chosen to allow an exploratory comparison of immunogenicity 28 days after the third administration in Stage 2 (Day 197), between participants receiving full dose of candidate iNTS-TCV vaccine and separate full doses of iNTS-GMMA and TCV vaccines, with respect to Anti-*S. Typhi* Vi Ag total IgG, Anti-*S. Typhimurium* O Ag total IgG, Anti-*S. Enteritidis* O Ag total IgG.

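### The MMRM applies one baseline slope to all five visits; a baseline-by-visit term would protect precision at Day 197 at almost no cost

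*SAP*

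**What the plan says.** SAP 15 compares full-dose iNTS-TCV with the separate vaccines "at Day 29, Day 57, Day 85, Day 169 and Day 197" in one repeated-measures model fitted to both stages. The prose lists fixed effects for center, treatment, time point, treatment by time point and center by treatment, then "center*treatment, baseline immunogenicity value as covariate, and a repeated time point effect within a participant under an unstructured covariance matrix". The code agrees: "model aval=center trta avisit trta*avisit center*trta baseline/ddfm=satterth", with "repeated avisit/subject=subjid type=un group=trta" giving each treatment its own unstructured 5 x 5 residual matrix, and "lsmeans trta*avisitn/pdiff cl alpha=0.05" for the visit-wise contrasts. The summary table at the end of SAP 15 also lists baseline once. The SAP allows other covariance structures and a transformation, but no other form for baseline.

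Protocol 9.2 says that "the sample size was chosen to allow an exploratory comparison of immunogenicity 28 days after the third administration in Stage 2 (Day 197"). Protocol 9.4.2 describes an ANOVA for each considered time point with vaccine group and center as effects, so the constraint across visits enters with the SAP. SAP 15 also plans an unadjusted GMC ratio at every visit, with treatment as the only term.

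**The concern.** With treatment by visit in the model and a single baseline term, the adjusted contrast at a visit is the difference in means minus the common slope times the chance baseline difference between arms. If the true slope at that visit differs from the common slope, the imbalance is partly left in or over-corrected, and the contrast varies more from trial to trial than it need do.

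The five visits span three doses. The relation to the Day 1 value may well not be the same before and after boosting. Day 197 comes after the last dose and is the visit that Protocol 9.2 ties to the sample size. At stake is the precision of the adjusted Day 197 ratio.

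**Working it through.** **The plan's own figure.** Protocol 9.2: "A total of 155 participants are planned to be randomized to achieve at least 133 evaluable participants", with 12% dropout in each group. Rounding 0.88 x n down in each of the nine groups (4, 4, 2, 16, 16, 8, 45, 45, 15) gives 3 + 3 + 1 + 14 + 14 + 7 + 39 + 39 + 13 = 133, as stated. The MMRM arms then have about 14 + 39 = 53 evaluable participants each. The documents give no SD, correlation between visits or baseline slope, so everything below is an assumed range.

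**Formulas.** Let b hold the five visit-specific slopes, S the residual covariance, sB the baseline SD and s197 the Day 197 residual SD. With complete data:

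- Common slope: bc = 1'S⁻¹b / 1'S⁻¹1. Re-estimating the unstructured matrix around the misfit leaves this value unchanged.
- Day 197 contrast variance is proportional to s197² + (b197 - bc)²sB² with the common slope, s197² + b197²sB² with no adjustment, and s197² with visit-specific slopes.
- With positive slopes, the common slope is worse than no adjustment exactly when bc > 2 x b197.

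**Constant total SD.** Inputs: baseline SD and total SD 1, slopes falling linearly over the five visits, residual correlation 0.5 to 0.7 between all visits. Variances are relative to visit-specific slopes.

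| Baseline correlation, Day 29 to Day 197 | bc | 2 x b197 | Common slope | Unadjusted | SE, common / unadjusted |
|---|---|---|---|---|---|
| 0.5 to 0.3 | 0.417-0.433 | 0.60 | 1.01-1.02 | 1.10 | 0.96 |
| 0.7 to 0.35 | 0.606-0.675 | 0.70 | 1.07-1.12 | 1.14 | 0.97-0.99 |
| 0.6 to 0.2 | 0.471-0.533 | 0.40 | 1.08-1.12 | 1.04 | 1.02-1.04 |
| 0.8 to 0.3 | 0.737-0.864 | 0.60 | 1.21-1.35 | 1.10 | 1.05-1.11 |

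Worked example, 0.6 to 0.2 with residual correlation 0.5: the visit weights are 0.378, 0.246, 0.168, 0.119 and 0.089, so bc = 0.471. Then 1 + (0.471 - 0.2)²/0.96 = 1.08, against 1 + 0.2²/0.96 = 1.04 unadjusted.

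**Equal residual SDs.** Under compound symmetry each visit has weight 0.20, and bc is the plain mean of the slopes. For 0.8 to 0.3, bc = 0.55, and the relative variance is 1 + 0.25²/1 = 1.06 at residual SD 1, or 1 + 0.25²/0.81 = 1.08 at residual SD 0.9. The other three cases give 1.01 to 1.04 at residual SD 1. None of the four is worse than no adjustment; 0.6 to 0.2 is a tie (bc = 0.40 = 2 x 0.2). Steeper or non-linear falls can still lose to it: slopes .7, .6, .4, .3, .2 give an SE ratio to unadjusted of 1.01, and .7, .5, .3, .2, .1 give 1.03.

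**Residual SD falling after boosting.** Weight moves to Day 197. With the SD falling from 1.0 to 0.7 and the same residual correlations, the relative variance in the four cases is about 1.01 or less in most settings and 1.02 at most.

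**Stable slope of 0.4.** bc equals b197. There is no loss, and the SE is 0.91-0.93 of the unadjusted SE.

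**Simulation.** 1000 trials per scenario, 53 per arm, center in the model, group-specific unstructured covariance, residual correlation 0.5. Each SD carries Monte Carlo error of about 1/√2000 = 2.2%.

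| Slopes (SD pattern) | SD, common | SD, unadjusted | SD, visit-specific |
|---|---|---|---|
| .7 to .2 (constant total SD) | 0.213 | 0.198 | 0.196 |
| .7 to .2 (equal residual SD) | 0.192 | 0.185 | 0.185 |
| .7 to .1 (constant total SD) | 0.217 | 0.190 | 0.192 |
| .6 to .3 (constant total SD) | 0.189 | 0.194 | 0.186 |
| Flat at .4 | 0.192 | 0.211 | 0.193 |

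In the first two rows the mean model-based SE was 0.206 and 0.201 against empirical 0.213 and 0.192, so the reported error is about right.

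**The case against.** The strongest defence is that the loss depends on inputs that the documents do not contain. A reader might infer that the early visits set the common slope, so that it must be too large at Day 197. The model does not imply this. The weights follow the residual covariance: early visits dominate when total SD is constant and the slope decays, all visits count equally under equal residual SDs with compound symmetry, and Day 197 can carry the largest weight if spread narrows after boosting. A reader might also infer that the planned adjustment is generally worse than none. In the two milder cases of the first table it is better.

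Steep decay is not documented either. Protocol 5.2 excludes prior typhoid vaccination and recent culture-confirmed *Salmonella*, and values below the cut-off become half the cut-off, so low slopes are plausible, at least for Vi. With slopes of .2 to .1 the SE ratio to unadjusted is 0.99-1.00 and nothing is at stake. That stands, though only culture-confirmed exposure is excluded, and Protocol 4.2 gives environmental exposure as a reason for studying both settings. Low slopes for the O antigens in Malawi are therefore not assured.

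It also stands that comparisons are exploratory and unpowered (Protocol 9.1 and 9.6.2), that no decision rule uses the MMRM, and that the sample-size statement concerns Stage 2 alone while the model pools both stages. None of this is a reason to keep one slope, because the pattern cannot be known in advance and the more flexible model does not depend on it.

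**Conclusion.** The constraint is real and appears in the prose, the code and the summary table. Its consequence is possible lost efficiency at Day 197. Under the assumptions above the variance penalty against visit-specific slopes is 1-2% for mild decay and 21-35% for the steepest decay at constant total SD. It is up to about 8% with equal residual SDs, close to zero if residual SD falls, and zero if the slope is stable. The adjusted ratio is less precise than the unadjusted one only when the common slope exceeds twice the Day 197 slope.

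It would be wrong to conclude that the comparison is biased or invalid: allocation is randomised, the unstructured covariance absorbs the misfit, and the simulated SEs were close to the empirical ones. The point is a low-severity, inexpensive improvement.

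**What to change.** Add baseline by time point to the list of fixed effects in SAP 15 and to its summary table, and add `baseline*avisit` to the MODEL statement. State that the covariate is the Day 1 value for every visit, on the same log10 scale as the response. SAP 6.5 defines baseline in two ways (Day 1, and before each vaccination), and SAP 15 does not say which the MMRM uses. The rest of the model can stay.

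The cost is four more parameters (five slopes in place of one) with about 106 participants, and no new data. If the slope is in fact constant, the loss is negligible (simulated Day 197 SD 0.193 against 0.192), and likewise if it is near zero.
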